4.6.1.1. Safety Run-in and Part 2, Arm A (Plamotamab, Tafasitamab and Lenalidomide)

Plamotamab is known to cause CRS. CRS has not been observed in clinical trials of tafasitamab and lenalidomide. However, lenalidomide, through its potential to activate T cells, may potentiate CRS in combination with plamotamab. In addition, to avoid the overlap of CRS caused by plamotamab with tafasitamab-induced, infusion-related reactions, plamotamab must always be given after tafasitamab if administered on the same day. See Section 4.7 for dose modification of lenalidomide and plamotamab in the instance of CRS.

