- Note that older subjects or those with significant comorbidities may be at higher risk of decompensation in this situation. When reactions occur in these vulnerable subjects, or in the case of rapidly progressing reactions, consider treatment with tocilizumab 8 mg/kg IV over 1 hour, with or without additional dexamethasone 10 to 20 mg IV (or equivalent).

Grade 3 and 4

- Stop the infusion and disconnect the infusion tubing from the subject.
- Administer additional dexamethasone 10 mg intravenously.
- Immediately give aggressive supportive care. Use pressors, fluids, oxygen, epinephrine or bronchodilators, ventilatory support, antipyretics, and analgesics as indicated.
- Treatment with tocilizumab, 8 mg/kg IV over 1 hour ([Hallek, 2018](#)), is encouraged for CRS due to the high risk of progression and permanent organ dysfunction.
- Hospital admission for observations is almost always indicated, usually to an intensive care unit, since an initial appearance of improvement may quickly yield to rapid decompensation.
- Subjects with Grade 3 CRS or infusion reaction may be rechallenged once resolved as described in [Section 4.7](#) and [Table 8](#). Subjects with recurrent Grade 3 or any Grade 4 reaction should not receive further plamotamab treatment but will continue to be followed on the protocol (ie, followed for long-term survival).
- Obtain an unscheduled blood sample for cytokine analysis during the event and approximately 4 hours later, unless scheduled cytokine monitoring is already in progress on the same visit day.
- Obtain an unscheduled sample for anti-drug antibodies (ADA) testing as close to the onset of the event as possible, at the resolution of the event, and approximately 28 days

following the event, unless scheduled cytokine monitoring is already in progress on the same visit day.

- Notify the Xencor Medical Monitor immediately.

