Infusion-related reactions	Grade 2 (moderate)	
 • Interrupt infusion of tafasitamab or plamotamab immediately and manage signs and symptoms. • Once signs and symptoms resolve or reduce to Grade 1, resume infusion at no more than 50% of the rate at which the reaction occurred. If the subject does not experience further reaction within 1 hour and vital signs are stable, the infusion rate may be increased every 30 minutes as tolerated to the rate at which the reaction occurred. • Dosing of other study medications is not modified.
	Grade 3 (severe)	
 • Interrupt infusion of tafasitamab or plamotamab immediately and manage signs and symptoms. • Once signs and symptoms resolve or reduce to Grade 1, resume infusion at no more than 25% of the rate at which the reaction occurred. If the subject does not experience further reaction within 1 hour and vital signs are stable, the infusion rate may be increased every 30 minutes as tolerated to a maximum of 50% of the rate at which the reaction occurred. • If the reaction returns after the rechallenge, stop the infusion immediately. • Dosing of other study medications is not modified.
	Grade 4 (life-threatening)	
 • Stop the infusion immediately and permanently discontinue: 
 – Tafasitamab if during or immediately following tafasitamab infusion. – Plamotamab if during or immediately following plamotamab infusion.
Cytokine release syndrome	Grade 2 (moderate)	
 • Interrupt plamotamab infusion immediately and manage signs and symptoms (see Section 4.6.1.6). • Once signs and symptoms resolve or reduce to Grade 1, resume plamotamab infusion at no more than 50% of the rate at which the reaction occurred. If the subject does not experience further reaction within 1 hour and vital signs are stable, the infusion rate may be increased every 30 minutes as tolerated to the rate at which the reaction occurred. • Tafasitamab and lenalidomide dosing is not modified.
	Grade 3 (severe) & Grade 4 (life-threatening)	
 • Interrupt plamotamab infusion immediately and disconnect infusion tubing from subject. Manage signs and symptoms (see Section 4.6.1.6). • The next scheduled dose of plamotamab will be given at 75% of the previous dose, unless the reaction occurred

Adverse Reaction	Severity	Dosage Modification

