		
on the C1D1 dose, in which case 100% of the previous dose may be given.
 
 • For subsequent plamotamab infusions, if: 
 – Toxicity does not recur or recurs at a Grade 1 severity, escalate to full dose of plamotamab at the time of the next dose. – Toxicity recurs at a Grade 2 severity, maintain 75% dosing of plamotamab. – Toxicity recurs at \geq Grade 3 severity at any time or if a Grade 2 takes more than 10 days to resolve to \leq Grade 1, discontinue plamotamab permanently. • Lenalidomide is also modified if a \geq Grade 3 CRS event occurs: 
 – During the first 5 doses of plamotamab: Reduce current dose of lenalidomide by 10 mg (or to 5 mg if currently at 10 mg) for subsequent doses until C4D1, when lenalidomide may be increased back to the dose prior to CRS. If CRS recurs at \geq Grade 2 on subsequent reduced dose lenalidomide, permanently discontinue lenalidomide. – After the first 5 doses of plamotamab: Reduce lenalidomide by 10 mg (or to 5 mg if currently at 10 mg) for all subsequent doses. If CRS recurs at \geq Grade 2 on subsequent reduced dose lenalidomide, permanently discontinue lenalidomide. • Tafasitamab dose is not modified.
Myelosuppression	Platelet count of less than 50,000/ μ L	
 • Withhold plamotamab, tafasitamab, and lenalidomide and monitor CBC weekly until platelet count is 50,000/μL or higher. • Resume plamotamab and tafasitamab at the same dose and lenalidomide at a reduced dose. Refer to lenalidomide prescribing information for dosage modifications. • If recurrence, repeat drug withholding and lenalidomide reduction steps until minimal lenalidomide dose is reached per lenalidomide prescribing information. • If recurrence at minimal lenalidomide dose, repeat drug withholding step (first bullet above) then reduce the next scheduled plamotamab dose to 75% of the previous dose.

Adverse Reaction	Severity	Dosage Modification

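### After a first Grade 4 CRS event, Table 8 gives a further plamotamab dose while Section 4.6.1.6 forbids one

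*Protocol*

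**What the plan says.** Two parts of the protocol tell a site what to do with plamotamab after severe CRS. Both apply in Part 1 and in Part 2 Arm A.

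**Section 4.6.1.6, Grade 3 and 4 guidance.** It separates the two grades. For Grade 3: "Subjects with Grade 3 CRS or infusion reaction may be rechallenged once resolved as described in" Section 4.7 and Table 8. For Grade 4: "Subjects with recurrent Grade 3 or any Grade 4 reaction should not receive further plamotamab treatment"; these subjects stay in follow-up only.

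**Section 4.7, Table 8, CRS.** One row covers both grades. "The next scheduled dose of plamotamab will be given at 75% of the previous dose, unless the reaction occurred" "on the C1D1 dose, in which case 100% of the previous dose may be given". The row then sets out later infusions. The favourable branch reads "Toxicity does not recur or recurs at a Grade 1 severity, escalate to full dose of plamotamab at the time of the next dose". A Grade 2 recurrence keeps the 75% dose. Permanent discontinuation follows only a recurrence at Grade 3 or higher, or a Grade 2 that takes more than 10 days to settle. The row also reduces lenalidomide after CRS of Grade 3 or higher and ends with "Tafasitamab dose is not modified".

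**Cross-references.** Section 4.6.1.1 tells sites: "See Section 4.7 for dose modification of lenalidomide and plamotamab in the instance of CRS". Section 4.6.1.6 sends only Grade 3 to Table 8. The Table 8 row points back to Section 4.6.1.6, but only for managing signs and symptoms.

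**The concern.** After a first Grade 4 CRS event the site and the medical monitor hold two written instructions that cannot both be followed. One ends plamotamab. The other directs a next dose and can lead back to full dose.

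On the protocol's grading (Table 4), Grade 4 CRS means several vasopressors or positive-pressure ventilation, so this is a question of subject safety. The triplet had not been given to humans before (Section 4.6), and Section 4.6.1.1 warns that lenalidomide may potentiate CRS. Phase 1 monotherapy rates may therefore understate the risk.

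There is also a labelling problem. Section 4.6.1.3 notes that CRS and infusion reactions share some manifestations, and Section 10.2.3.1 grades both on the ASTCT scale. Table 8 stops plamotamab for good after a Grade 4 infusion reaction to it ("Plamotamab if during or immediately following plamotamab infusion"). A similar Grade 4 event could then end treatment under one label and continue it under the other.

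**Working it through.** The plan states no figure to reproduce. The check compares the two rules, then works out the doses and the likely frequency.

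**1. The rules side by side**

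| Event | Section 4.6.1.6 | Table 8, CRS row | Agree? |
|---|---|---|---|
| First Grade 3 | Rechallenge allowed, per Table 8 | Next dose at 75% (100% allowed after C1D1) | Yes |
| Recurrent Grade 3 | No further plamotamab | Permanent stop | Yes |
| First Grade 4 | No further plamotamab | Next dose at 75% (100% allowed after C1D1) | **No** |

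A first Grade 4 event meets neither of Table 8's conditions for stopping, because both concern later infusions.

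**2. Comparable Grade 4 rows of Table 8**

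- Infusion reaction to plamotamab: permanent stop, which matches Section 4.6.1.6.
- Neurotoxicity: permanent stop, which matches Section 4.6.1.7.

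Among these three acute Grade 4 toxicities, CRS is the only one for which the text and the table disagree.

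**3. Next dose after a first Grade 4 CRS event**

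Doses come from Table 3. Under Table 8, next dose = 0.75 × previous dose, except after C1D1, when 1.00 × previous dose is permitted.

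| Dose at which CRS occurred | Table 8 | Section 4.6.1.6 |
|---|---|---|
| C1D1, 0.8 mg | up to 1.00 × 0.8 = 0.8 mg | none |
| C1D8, 2 mg | 0.75 × 2 = 1.5 mg | none |
| 20 mg | 0.75 × 20 = 15 mg | none |
| 35 mg (Cohort 1B) | 0.75 × 35 = 26.25 mg | none |
| 50 mg (Cohort 1B) | 0.75 × 50 = 37.5 mg | none |

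**4. How often it could arise**

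- Section 2.4.1: 4 of 80 Phase 1 lymphoma subjects had CRS of Grade 3 or higher, all with the first infusion. No Grade 4 count is given, so the observed Grade 4 rate lies between 0/80 = 0% and 4/80 = 5.0%.
- Section 2.4.2: in the flat step-up cohort all CRS was Grade 1 or 2, so 0 of 14 subjects had Grade 3 or higher. The exact two-sided 95% upper limit is 1 − 0.025^(1/14) = 0.232, or 23.2%. This limit is for Grade 3 or higher, not Grade 4; it shows only that 14 subjects cannot exclude severe CRS.
- Planned plamotamab exposure: at least 40 subjects in Part 1 and about 200/2 = 100 in Arm A. SAP Section 1 reports termination after 3 subjects were enrolled.

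**The case against.** The textual conflict is not disputed. The case on the other side is that it matters less, and is less one-sided, than it looks.

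- **Table 8 may be the operative rule.** Section 4.6.1.4 puts local CRS procedures first and offers the protocol's guidance as a fallback. Section 4.7 treats Section 4.6 as additional guidance and says Table 8 holds the dose modifications by grade. This is real evidence about hierarchy, but it does not settle the matter. The bar in Section 4.6.1.6 is itself a dosing instruction, and nothing says Table 8 overrides it. It also means a site using its own CRS procedure might never read the Grade 4 stop.
- **Other Grade 4 rows allow resumption.** Febrile neutropenia also merges Grades 3 and 4 and resumes at the same dose. Grade 4 liver toxicity forces a permanent stop only if it lasts more than 3 days. This weakens the argument from pattern. These are different toxicities, however, and no stopping rule elsewhere contradicts those rows.
- **No site is forced to re-dose.** Section 6.3.1 lets the investigator withdraw treatment for an unacceptable event, and Section 4.6.1.6 requires immediate notice to the medical monitor at Grade 3 and 4. Both limit the risk. Neither says which rule applies.
- **The larger doses are hypothetical.** Every Phase 1 lymphoma event of Grade 3 or higher came with the first infusion, so the 15, 26.25 and 37.5 mg cases have no such event behind them. That stands. The first infusion is, however, where Table 8 is most permissive.
- **Intent is not documented.** That also stands: treating the Table 8 row as the error is an inference.

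**Conclusion.** The protocol contradicts itself on plamotamab after a first Grade 4 CRS event, and it should be corrected. The conflict lies in current text, and Table 8 names Grade 4 explicitly. For a subject who has the event, the difference is no further plamotamab against a next dose of up to 0.8 mg after C1D1, or 1.5 to 37.5 mg after later doses, with possible return to full dose.

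The number affected is unknown and may be near zero: 0% to 5.0% observed at Grade 4 in Phase 1, and only 3 subjects enrolled before termination. The finding rests on the seriousness of the event and the clarity of the conflict, not on frequency. That stopping was the intended rule is inferred from Section 4.6.1.6 and from the Grade 4 infusion-reaction and neurotoxicity rows. No efficacy analysis or error rate is involved.

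**What to change.** Split the CRS row of Table 8 that combines Grades 3 and 4.

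- **Grade 3:** keep the present text.
- **Grade 4:** stop the infusion immediately, disconnect the tubing, manage per Section 4.6.1.6, and permanently discontinue plamotamab. Repeat unchanged both lenalidomide instructions for CRS of Grade 3 or higher (during and after the first 5 plamotamab doses) and the line leaving tafasitamab unmodified.

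Sections 4.6.1.6 and 4.6.1.2 need no change. The sponsor should confirm that stopping is what it intended. It may also review the lenalidomide reduction once plamotamab has stopped, since Section 4.6.1.1 bases the concern on the combination. Carrying that text over simply preserves the current rule.

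The edit is one table row in language the protocol already uses, with no extra data, visits or subjects. As an amendment it needs IRB/IEC approval before use (Section 12.3), across up to 120 planned sites. Because the rule applies from the first plamotamab dose in Part 1, it should not wait for the revision planned before Part 2. With the study terminated, the correction matters mainly if this dosing text is used again.

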Day -8 and -4 (Priming Dose)	Cycle 1 Days 1, 8, 15, 22	Cycle 2 Days 1, 8, 15, 22	Cycle 3 Days 1, 8, 15, 22	Cycle 4 and Subsequent Q2W Dosing
12 mg/kg	12 mg/kg	12 mg/kg	12 mg/kg	12 mg/kg

Q2W = every two weeks.

Lenalidomide: All subjects will receive lenalidomide and self-administer a starting dose of 25 mg oral lenalidomide daily on Days 1 to 21 of each cycle. No more than 21 doses of lenalidomide will be dispensed per cycle; lenalidomide can be given for only up to a total of 12 cycles. Investigators will follow the package insert or SmPC for recommended medications for venous thromboembolic event prophylaxis and dosing modifications. It is recommended that subjects take oral (PO) lenalidomide in the evening about the same time each day, with or without food. Subjects are to swallow lenalidomide capsules whole with water. When ingesting, the capsules should not be opened, broken, or chewed. Treatment with lenalidomide may be modified in a deescalating fashion or discontinued based upon clinical and laboratory findings. Detailed dose modification guidelines to manage hematologic and/or other toxicities are provided in the relevant sections of the protocol.

Study Drug Use in Part 1: Single-arm, Two-cohort, Safety Run-in

This first part of the study is designed to establish a dose of plamotamab with an acceptable safety profile when given in combination with the other 2 drugs.

- Part 1, Cohort 1A treats subjects with the triple combination at plamotamab dose level -1.
- Part 1, Cohort 1B commences enrollment after Cohort 1A completes enrollment. Cohort 1B treats subjects with the triple combination at plamotamab dose level 1.

- An initial safety evaluation is conducted after all subjects in Cohorts 1A and 1B either receive treatment, at a minimum, through C4D28 or are discontinued prior to C4D28 due to an AE or progressive disease.

Study Drug Use in Part 2: Two-Arm, Open-label, Randomized, Efficacy and Safety

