4.7. Dose Modification Guidelines

Treat subjects experiencing a significant toxicity with standard medical interventions (eg, use of filgrastim to treat neutropenia, acetaminophen for fever) as appropriate. For infusion reactions/CRS and neurotoxicity management, Investigators may use their standard treatment practices, and for additional guidance, see [Section 4.6](#).

In general, if a > Grade 2 toxicity prevents dosing > 14 days and/or if 2 consecutive doses are missed (this applies to weekly and Q2W dosing), the subject may require discontinuation from the plamotamab or tafasitamab treatment. Subjects may reinitiate study drug, even after 2 or more missed consecutive doses of plamotamab or tafasitamab, if the Investigator determines that the benefit outweighs the risk and the toxicity (if applicable) can be controlled by concomitant medication or other means. Medical Monitor approval is required for delays of > 14 days and/or 2 consecutive doses.

During weekly dosing of plamotamab and/or tafasitamab, if a subject's dose is held for ≥ 7 days, it should be considered missed. During Q2W dosing of plamotamab and/or tafasitamab, if a subject's dose is held for ≥ 14 days, it should be considered missed. If a subject's dose is given out of window or delayed for safety concerns, including AEs, it is not considered a protocol deviation.

Plamotamab may be resumed after prolonged dose delay for more than one cycle for reasons other than toxicity (eg, comorbidity, pseudoprogression, or delayed response). Resuming initial treatment course may be allowed on a case-by-case basis if the Investigator and the Sponsor consider this in the best interest of the subject. As a safety measure, the dose may be lowered to the priming dose for re-titration. Study assessments, including local and/or central labs, are to be collected per the Schedule of Assessments.

For toxicities that could overlap (eg, CRS, infusion reaction, hematologic toxicities), detailed dose modifications by grade are presented in [Table 8](#) below:

Table 8: Dose Modifications for Select Toxicities

Adverse Reaction	Severity	Dosage Modification

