	
Neutrophil count of 1,000/μL or less for at least 7 days OR
 
Neutrophil count of 1,000/μL or less with an increase of body temperature to 100.4°F (38°C) or higher OR
 
Neutrophil count less than 500/μL
	
 • Withhold plamotamab, tafasitamab, and lenalidomide and monitor CBC weekly until neutrophil count is 1,000/μL or higher. • Resume plamotamab and tafasitamab at the same dose and lenalidomide at a reduced dose. Refer to lenalidomide prescribing information for dosage modifications. • If recurrence, repeat drug withholding (first bullet above) and lenalidomide reduction steps until minimal lenalidomide dose is reached per lenalidomide prescribing information. • If recurrence at 5 mg lenalidomide, repeat drug withholding steps then reduce the next scheduled plamotamab dose to 75% of the previous dose.
Febrile Neutropenia	Grade 3 (severe) & Grade 4 (life-threatening)	
 • Withhold plamotamab, tafasitamab, and lenalidomide and monitor CBC until neutrophil count is Grade \leq 1. • Once subject is afebrile, off antibiotics and neutrophil count is Grade \leq 1, resume all therapy at the same dose and schedule.
Neurotoxicity	Grade 3 (severe)	
 • Withhold plamotamab and manage signs and symptoms (see Section 4.6.1.7) until the toxicity has recovered to \leq Grade 1 (mild) and has remained at \leq Grade 1 for at least 3 days before restarting therapy. • Reduce next scheduled plamotamab dose to 75% of the previous dose. If \geq Grade 2 toxicity does not recur, escalate plamotamab to full dose in subsequent administrations. • If \geq Grade 2 toxicity recurs at 75% dose, or if $<$ Grade 2 toxicity takes more than 7 days to resolve, permanently discontinue plamotamab. • Tafasitamab and lenalidomide dosing is not modified.
	Grade 4 (life-threatening)	
 • Stop infusion immediately, if still infusing and permanently discontinue plamotamab.
AST, ALT, bilirubin, and alkaline phosphatase in the absence of CRS	Grade 3 (severe)	
 • Withhold plamotamab and manage signs and symptoms until the toxicity has recovered to \leq Grade 1 (mild) or baseline. • If a Grade 3 liver toxicity persists $>$ 14 days and/or 2 consecutive doses are missed and the toxicity cannot be attributed to another cause, permanently discontinue plamotamab. • Tafasitamab and lenalidomide dosing is not modified.

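### Table 8 gives incompatible lenalidomide restart doses for an event that meets both the neutrophil row and the Grade 3/4 Febrile Neutropenia row, and no printed text says which row governs

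*Protocol*

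**What the plan says.** Section 4.7 presents Table 8 as the place to resolve overlapping toxicity: "For toxicities that could overlap (eg, CRS, infusion reaction, hematologic toxicities), detailed dose modifications by grade are presented in" that table.

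**Neutrophil row (under Myelosuppression).** It has three alternative triggers: a count of 1,000/µL or less for at least 7 days; a count of 1,000/µL or less "with an increase of body temperature to 100.4"°F (38°C) or higher; or a count below 500/µL. All three drugs are withheld, and sites are told to "monitor CBC weekly until neutrophil count is 1,000"/µL or higher. The restart instruction is "Resume plamotamab and tafasitamab at the same dose and lenalidomide at a reduced dose", with the reader referred to the lenalidomide prescribing information for the step. On recurrence the hold and the lenalidomide reduction are repeated. At the end of that path: "If recurrence at 5 mg lenalidomide, repeat drug withholding steps then reduce the next scheduled plamotamab dose to 75% of the previous dose".

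**Febrile Neutropenia row, Grade 3 and Grade 4.** All three drugs are withheld. The restart condition is "Once subject is afebrile, off antibiotics and neutrophil count is Grade" 1 or lower. The instruction is then to "resume all therapy at the same dose and schedule". No recurrence rule is printed.

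On lenalidomide generally, the Synopsis and Section 7.1.3 say "Investigators will follow the package insert or SmPC for recommended medications for venous thromboembolic event prophylaxis and dosing modifications" (Section 7.1.3 adds the label citations). Both also say that the detailed guidance for hematologic toxicity is in the protocol.

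**The concern.** The neutrophil row carries its own fever trigger, so it is not simply the row for afebrile neutropenia. An event can meet that trigger and also be graded as febrile neutropenia of Grade 3 or 4. The two rows then give opposite answers on whether lenalidomide comes back at the dose in use before the event or at a lower one.

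This is a dosing rule for a serious toxicity. Section 4.6 says the triple combination had not been tested in humans, and Section 4.6.3 warns that neutrophil decreases may worsen when the drugs are combined. All subjects receive lenalidomide, so Part 1 and both Part 2 arms are exposed to the ambiguity. Two sites could treat the same event differently and both be following Table 8. Lenalidomide dose intensity in Part 1 is itself a secondary endpoint (Section 4.2.2, item 8), so the recorded doses would partly depend on which row a site happened to read.

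**Working it through.** The plan gives no figure to reproduce. The check sets the two rows side by side for one event that meets both triggers, and then looks for text that ranks them.

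| | Neutrophil row | Febrile Neutropenia row |
|---|---|---|
| During the event | Hold all three drugs | Hold all three drugs |
| Restart when | Count is 1,000/µL or higher | No fever, no antibiotics, neutrophils Grade 1 or lower |
| Plamotamab at first restart | Same dose | Same dose |
| Tafasitamab at first restart | Same dose | Same dose |
| Lenalidomide at first restart | Reduced dose | Same dose |
| On recurrence | Repeat the hold and step lenalidomide down again; at 5 mg, plamotamab to 75% | No step printed; reapplied, it returns to the same dose |

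**Dose.** At first restart the rows agree on 2 of 3 drugs and conflict on 1, lenalidomide.

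**Timing.** The restart conditions differ, and this affects all three drugs.

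**Recurrence.** Only one row has a step-down.

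**Search for a rule of precedence.**

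- The introduction to Table 8 in Section 4.7 sends overlapping hematologic toxicities to the table without ordering its rows.
- The note below Table 8 allows case-by-case decisions for other Grade 3 or higher events, meaning those the table does not list. Both rows are listed.
- Sections 4.6.3 and 4.6.3.1 mention institutional guidelines and a possible delay until counts are at least Grade 2, and then refer to Section 4.7.
- Section 4.6.3.2 sends Arm B to the tafasitamab prescribing information, and then to Section 4.7.
- The Synopsis and Section 7.1.3 cite the lenalidomide label and also point back to the protocol. Section 2.4.3 refers to the labels in general terms.

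None of these chooses between the rows.

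**Consistency within the table.** A count below 500/µL without fever falls only under the neutrophil row and requires a lenalidomide reduction. If the event becomes Grade 3/4 febrile neutropenia, the second row allows a return to the same dose. The more serious presentation can therefore receive the more lenient restart.

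**Size.** The reduction step for neutropenia is not printed. The 10 mg step elsewhere in Table 8 belongs to cytokine release syndrome and cannot be borrowed. No first-restart figure is computed.

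**The case against.** The strongest reply is that the label decides. Lenalidomide is the only drug whose restart dose conflicts, investigators are told to follow its label for dosing modifications, and the neutrophil row refers to it directly. If the label addresses neutropenia with fever, a site may have a governing instruction. This part stands: the finding is that the protocol prints no tie-breaker, and what the labels say cannot be checked here. It does not settle the matter, because the same sections point back to the protocol and the Febrile Neutropenia row gives its own explicit instruction without citing the label.

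A second reply is that sites would not diverge unseen. Section 4.7 requires Medical Monitor approval for delays of more than 14 days and/or 2 consecutive doses, and waiting for fever and antibiotics to end could trigger that contact. This is a partial safeguard. It does not set the lenalidomide dose.

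Three stronger readings are tempting and are not supported:

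- A reader might infer a 25% difference in plamotamab dose: 0.75 × 20 mg = 15 mg, or 0.75 × 50 mg = 37.5 mg. That step applies only to a subject already at 5 mg lenalidomide, in Part 1 or Arm A. A site that always used the Febrile Neutropenia row would not bring a subject to 5 mg through these events. The figures do not measure the first-restart conflict.
- A reader might infer that every neutropenic fever is affected. The conflict covers only events that also meet Grade 3/4 febrile neutropenia, whose definition the documents do not print.
- A reader might infer an effect on the trial's results. The SAP (Sections 1, 4.1 and 7) reports early termination with 3 subjects enrolled and listings only, and the documents give no rate for the overlapping event.

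**Conclusion.** The inconsistency is real and should be fixed. For an event that meets both triggers, Table 8 gives incompatible lenalidomide restart doses (reduced versus same) and different restart conditions, and only one of the two rows has a step-down on recurrence. This is a contradiction between two stated rules rather than missing detail, and no printed text resolves it.

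No size is claimed for the first-restart difference, no frequency for the event, and no effect on any result. The conclusion rests on two assumptions: that some events meet both rows, which the wording allows since neither row excludes the other, and that the cited labels do not supply a ranking of the protocol's own rows. The first depends on a grading definition that is not printed, and the second cannot be verified from the documents.

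**What to change.** Make two wording changes in Table 8.

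1. In the Febrile Neutropenia row, keep the present restart condition. Replace "resume all therapy at the same dose and schedule" with the neutrophil row's instruction, "Resume plamotamab and tafasitamab at the same dose and lenalidomide at a reduced dose", and add that recurrences follow the neutrophil-row steps.
2. In the neutrophil row, add: *If the event is also Grade 3/4 febrile neutropenia, the Febrile Neutropenia row's restart condition applies.*

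The reduced dose is proposed as the default because the table already requires it for an afebrile count below 500/µL. Sponsor clinicians should confirm that choice.

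Two other repairs are less suitable. Deleting the fever trigger from the neutrophil row would not remove the overlap, since a febrile subject with a count below 500/µL still meets that row. Applying the stricter restart condition to every fever in the neutrophil row would reach events outside the overlap. Fever is part of cytokine release syndrome at onset (Section 4.6.1), so holds of all three drugs could lengthen without need.

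The cost is a protocol amendment with IRB/IEC approval before use (Section 12.3) and somewhat lower lenalidomide exposure after such events. The hold condition is the one the Febrile Neutropenia row already prints, although a site that would have followed the neutrophil row may wait longer. Because the study has stopped, the practical value is that the wording is not reused uncorrected.
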